10.4.3 ANALYSIS OF THE SECONDARY ENDPOINT(S)

QoL: An AHF SSU strategy of care will lead to significant improvement in QoL scores at 30 days post-discharge compared with usual care. QoL will be assessed with the KCCQ.⁵⁹

Sample Size Calculation: The standard deviation of 1-week KCCQ change after acute heart failure is 20.8.⁷³ Below are the numbers of subjects (both arms combined) required to detect various intervention effects with 80% power and type I error controlled at 0.05 (two-sided) in the table.

Similarly, the number of subjects (both arms combined) required to detect various effect size for caregiver burden (CB) with 80% power and type I error controlled at 0.05 (two-sided) is listed below. The effect size is defined as the difference in CB score divided by the standard deviation. It is a widely-used measure of treatment effect, which is used here because the standard deviation of CB in the target population if it has not been robustly studied. Because we changed CB scales, we will use established MCID for each established scale.

KCCQ: Sample size (both arms combined)	% of data attrition	Difference in KCCQ change
480	10%	5.3
360	33%	6.2
240	55%	7.6
120	78%	10.7

KCCQ QoL Analysis: The KCCQ will be compared between the two arms using the same method as in Aim 1. We will consider three ways of analysis with different outcomes based on KCCQ scores. First, we will exclude subjects who die without KCCQ in the analysis. Second, we will set KCCQ=0 for those who die without the 30-day KCCQ and include these people in the analysis. Third, we will create a composite binary endpoint of KCCQ<c or death, where c is a threshold. Chi-square test and logistic regression will be used to compare this outcome. We will select several relevant values for the threshold c and tabulate the results. The three analysis schemes allow us to understand how robust the comparison of KCCQ is with respect to different treatments of death.

Cost-Effectiveness Analysis:

To assess the effectiveness of short stay unit (SSU) management, we will analyze the patient outcomes as defined by cost, quality-of-life (QOL), medical utilization, and caregiver burden using regression analysis, and combine these results into a multifaceted incremental cost-effectiveness ratio (ICER).

$$ICER = \frac{C_{SSU} - C_H}{E_{SSU} - E_H}$$

Here, E_{SSU} and C_{SSU} are the effectiveness and cost, respectively, of the SSU, while the E_H and C_H are the effectiveness and cost of the hospital admission. The incremental cost effectiveness ratio allows us to estimate the additional cost associated with SSU treatment proportionate to the increased effectiveness of its patient outcome. We expect SSU treatment to dominate hospital admission, resulting in greater effectiveness at a lower cost.^{1,2} Therefore, we expect ICER to be negative, reflecting the cost savings of implementing SSU treatment.

Our goal is to evaluate the cost-effectiveness of the SSU strategy from a societal perspective, as we will account for the costs of care from both the hospital/insurer perspective and patient point-of-view. As discussed in more detail below, our primary challenges lie in obtaining accurate and complete costs incurred by the patient outside of the hospital setting. Given this potential limitation, at minimum, our CEA evaluation will be from the hospital/payer perspective.

We will use an episodic approach to costing, which accounts for any cost shifting to a later point in time. This is the preferred approach for the Centers for Medicaid and Medicare services. Specifically, we will examine the total cost of patient care from the index ED visit (study enrollment) for a period of 30 days. In the context of the episode, we will analyze the incidence of readmission, total days of hospitalization, utilization of outpatient care, total cost, and caregiver burden.

The outcome variables of interest are cost, effectiveness, and other characteristics of participant experience. Costs will be defined by total billable hospital costs (Table 1) and patient costs. Hospital costs include payments by insurance, patients, and third parties. While this type of cost information is most accurate for our purposes, it is also the most difficult to obtain. Recognizing the phenomenon of 'upcharging,' we will obtain hospital charges from each site as this is the easier data to acquire.

Given the difficulty of obtaining costs and payments, we will standardize hospitalization and SSU costs using Medicare reimbursement rates (See Sensitivity Analysis Section below). Patient costs will include self-reported out-of-pocket costs and time costs using a modified version of a previously published survey. (see attached) One limitation of self-reported data will be potential mismeasurement due to recall bias. Should the patient-completed survey lack a sufficient response rate for outpatient analysis, we will limit our analysis to the hospital portion of the treatment. Effectiveness will be defined by SF-12 and SF-6D metrics of patient self-reported QOL. The SF-12 has been previously used to evaluate outcomes for HF patients.³ Effectiveness in ICER computations is often measured using quality-adjusted life years (QALYs), defined as:

$$QALY = \sum_{t=t_0}^Z \delta^{t-t_0} q_t P_t$$

where P_t is the probability of surviving to each year t , q_t is the preference weight, and δ is the time-discounting factor. As the SF-12 does not allow direct assessment of QALYs, we will convert the score into a SF-6D preference based score using the six health dimension scores from the SF-12^{4,5} to generate the preference weights and probabilities necessary to conduct the cost-utility analysis. Since the participant will be completing the SF-12 survey at the beginning and end of the episode, all models estimating the effectiveness will include the baseline score in the vector of participant characteristics. Aside from cost and effectiveness, we will analyze the incidence of re-admission, the utilization of outpatient care, and caregiver burden, as detailed in our statistical analysis plan. While the incidence of re-admission will be obtained from both the electronic health record and patient self-report, the outpatient and caregiver burden are self-reported.

For each outcome variable of interest (patient costs, hospital costs, total episode costs, SF-12 scores, SF-6D scores, QALYs, incidence of readmission, total days of hospitalization, utilization of outpatient care, nursing care, and caregiver burden) we will estimate a predictive model accounting for the heterogeneity among participants in the intervention and control groups.

$$Y_i = \alpha + \beta_1 SSU_i + \beta_2 D_i + \beta_3 R_i + \beta_4 D_i * R_i + \beta_5 D_i * SSU_i + \beta_6 R_i * SSU_i + \beta_7 D_i * R_i * SSU_i + \gamma X_i + \delta H_h + \kappa_h + \tau_t + \varepsilon_i$$

where, Y_i is the outcome of interest for participant i described in the following paragraph. SSU_i is an indicator if the participant was assigned to the SSU treatment, D_i are the total number of hospital inpatient days, R_i is an indicator for a readmission. The interaction terms $D_i * R_i$ and $D_i * R_i * SSU_i$ differentiate between continuous inpatient days and inpatient days separated with a readmission, for hospital admission and SSU group respectively. The interaction terms $D_i * SSU_i$, and $R_i * SSU_i$ capture the effect of SSU on inpatient days and readmission rates. X_i is a vector of participant characteristics (age, gender, insurance status, etc.), H_h is a vector of hospital characteristics, κ_h , τ_t are hospital, and year fixed effects, and ε_i is an independent and identically distributed error term. The effect of the SSU assignment on the outcome measure will be captured by coefficients β_1 , β_5 , β_6 , β_7 , unbiased and consistent estimators of the intervention effect because of the random assignment of participants.

When estimating the re-admission rate, we will use a probabilistic model such as:

$$\Pr(R_i) = F(\alpha + \beta_1 SSU_i + \beta_2 D_i + \beta_3 D_i * SSU_i + \gamma X_i + \delta H_h + \kappa_h + \tau_t + \varepsilon_i)$$

where the probability of readmission will be a function of intervention status, SSU_i , days of inpatient care, D_i , the interaction between these, $D_i * SSU_i$, participant characteristics, X_i , vector of hospital characteristics, H_h , and fixed effects, κ_h , τ_t , and ε_i is an independent and identically distributed error term. The choice of the functional form for this model will depend on the incidence of readmission in the data

Random assignment to SSU will be tested in pre-analysis by comparing the means of the intervention and control group characteristics using t-tests, and probability of being assigned to intervention group conditional of participant characteristics, particularly health status.

Sensitivity Analysis for CEA

To test the robustness of our estimates, in view of the assumptions made about cost, the choice of effectiveness measure, and the probability specification function for readmission, we will re-evaluate our results with alternative definitions.

To test the sensitivity of ICER to definition of cost, we will construct a projected cost measure based on CMS reimbursement for ICD-10 and CPT codes for hospitalization and SSU participants. The benefits and shortcomings of this approach are outlined in Table 1. Should the SF-12 lack sufficient variability between SSU and hospitalized participants, converting the measure to SF-6D will reduce the remaining heterogeneity, magnifying the ICER cost estimate. We will repeat ICER with SF-12 to test the significance in the loss of heterogeneity due to conversion.

Table 1 Hospital Costs Reports

	Pros	Cons
1 Payments Payments received by hospitals from all sources	
 Most accurate reflection of costs of care. Cost for all types of insurance Includes patient share of cost 	
 Hospitals reluctant to report Does not include uncompensated care
2 Reimbursements from CMS Payments from CMS for Medicare and Medicaid patients	
 Accurate reflection of costs of care. Projected to non-CMS patients. 70% of all ED visits have Medicare or Medicaid as primary payer. 	
 Obtain claims report from CMS (?) Less accurate for non-CMS patients. Does not include patient share or uncompensated care.
3 Charges Charges presented by hospital for each procedure	
 Procedure specific charges Accurate reflection of the charges presented to insurance or CMS Hospitals more likely to report Includes all types of insurance, including uncompensated care. 	
 Charges to cost ratio may differ by treatment type Not an accurate reflection of the cost of care. Does not include patient share.
4 Projected costs By CPT and ICD-10 codes transformed	
 Approximate measure of CMS reimbursement 70% of all ED visits have Medicare or Medicaid as primary payer 	
 Lost accuracy of variation in cost Does not include patient share Less accurate for non-CMS patients

through CMS reimbursement rates.		
----------------------------------	--	--

When analyzing the re-admission rates, we will use a multinomial binary logistic function, estimating the odds ratio of any re-admission as a function of SSU status. We will also estimate the specification using a negative binomial generalized linear model with a log-link function, to analyze the effect of SSU on the number of re-admissions.

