4.2.2 SECONDARY ENDPOINTS

1) Quality of life as measured by Kansas City Cardiomyopathy Questionnaire 2) Cost effectiveness analysis between the two arms at 30 days.

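### The 30-day cost-effectiveness endpoint rests on a single ICER expected to be negative, with no rule for reporting dominance and no joint uncertainty method

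*Combined protocol and SAP*

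**What the plan says.** Section 4.2.2 lists as a secondary endpoint: "Cost effectiveness analysis between the two arms at 30 days". The method is in section 10.4.3 under Cost-Effectiveness Analysis.

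- **Summary measure.** Outcomes are analysed by regression, and the plan will then "combine these results into a multifaceted incremental cost-effectiveness ratio (ICER"). The formula is the cost difference (SSU minus hospital) divided by the effectiveness difference.
- **Expected result.** "We expect SSU treatment to dominate hospital admission, resulting in greater effectiveness at a lower cost". The next sentence reads: "Therefore, we expect ICER to be negative, reflecting the cost savings of implementing SSU treatment". No other guidance is given on reading the sign.
- **Horizon.** "we will examine the total cost of patient care from the index ED visit (study enrollment) for a period of 30 days".
- **Effect measure.** "Effectiveness will be defined by SF-12 and SF-6D metrics of patient self-reported QOL", with conversion to QALYs.
- **Component models.** For each outcome, including total episode cost, SF-12, SF-6D and QALYs, "we will estimate a predictive model accounting for the heterogeneity among participants in the intervention and control groups".
- **Sensitivity analysis.** The section opens: "To test the robustness of our estimates, in view of the assumptions made about cost, the choice of effectiveness measure, and the probability specification". It changes definitions and model forms. It also notes that if SF-12 differs little between the arms, conversion to SF-6D will enlarge the ratio, and it responds by repeating the ratio with SF-12.

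Neither section 10.4.3 nor the general approach in section 10.4.1 gives an interval or bootstrap for the ICER, a cost-effectiveness plane, net monetary benefit, a willingness-to-pay value, an acceptability curve or a rule for reporting dominance. The exploratory 90-day cost-effectiveness endpoint (section 4.2.3) has no separate method.

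**The concern.** A ratio of two differences carries useful information when both differences have the same sign, because it then states a price per unit of health gained or given up. When the signs differ, one strategy dominates, and the size of the ratio no longer ranks results. The sponsor expects exactly this case. The short horizon adds to the difficulty: 30 days can yield at most 30/365 = 0.082 QALY per patient, so the denominator is bound to be small, and a small change in it moves the ratio a long way.

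If the ratio were published alone, a reader could take a more negative value for a better result when, at the same saving, it reflects a smaller health gain. Without a joint measure of uncertainty, the report would also not say how sure one can be that SSU is cost-effective.

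**Working it through.** The documents give no ICER, cost difference, effect difference or power for this analysis, so there is no stated figure to reproduce. The check is algebra on the plan's own formula, followed by a simulation under stated assumptions.

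**Inputs**
- Cost difference: $3,600. This is the only SSU-versus-admission figure in the documents (section 2.2). It is a difference in charges from an earlier risk-matched, non-randomised comparison and serves here only as an illustration.
- Effect differences: assumed. Gains of 0.004, 0.002 and 0.0002 QALY correspond to utility differences, held for all 30 days, of 0.004 × 365/30 = 0.049, 0.024 and 0.0024.
- Willingness to pay (λ): assumed $50,000 per QALY.
- Evaluable patients: 240 per arm (section 10.5).

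**Formulae.** ICER = ΔC/ΔE. Incremental net monetary benefit: NMB = λ·ΔE − ΔC.

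| Case | ΔC ($) | ΔE (QALY) | ICER ($/QALY) | NMB ($) |
|---|---|---|---|---|
| A. Cheaper, largest gain | -3,600 | +0.004 | -900,000 | +3,800 |
| B. Cheaper, middle gain | -3,600 | +0.002 | -1,800,000 | +3,700 |
| C. Cheaper, smallest gain | -3,600 | +0.0002 | -18,000,000 | +3,610 |
| D. Dearer and worse | +3,600 | -0.002 | -1,800,000 | -3,700 |
| E. Cheaper but worse | -3,600 | -0.002 | +1,800,000 | +3,500 |

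1. **Ordering (A to C).** The saving is fixed. As the health gain falls, the ICER becomes more negative, while NMB falls as it should.
2. **Same value, opposite meaning (B and D).** Both give -$1.8M per QALY. NMB separates them.
3. **Sign and saving (E).** SSU saves money, yet the ICER is positive.

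These three results follow from the formula and hold on any effect scale, SF-12 included. Only the dollar sizes depend on the inputs. If a utility gain built up linearly over the 30 days instead of being held throughout, it would yield half the QALYs and every ratio would double.

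**How often sign and saving would part.** The simulation assumed a true saving of $3,600, independent normal errors, an SF-6D SD of 0.10 to 0.14 and a cost SD of $5,000 to $20,000. It gave the chance of an estimated saving together with a positive ICER:

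| True SF-6D difference | Chance |
|---|---|
| 0 | 49–50% |
| 0.01 | 13–22% |
| 0.02 | 1–6% |
| 0.03 | under 1% |

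A dearer-and-worse estimate arose in about 1% of simulated trials or fewer. Only if both true differences are zero are half of all negative ICERs of that kind.

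**The case against.** Three stronger readings are tempting, and the documents support none of them.

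- *The plan will read any negative ICER as a saving.* Section 10.4.3 argues the other way: it first expects SSU to dominate and then infers a negative ratio. That inference is valid, and no converse rule is stated.
- *A dominant result could not be told from a dominated one.* Costs and QALYs have their own models, so the analysts would know the sign of each difference before forming the ratio. If the true saving were near $3,600, a dominated estimate would also be rare.
- *The trial could not say how certain the conclusion is.* The patient-level data are to be collected. What is missing is a pre-specified method.

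Two further objections have force. The plan's own Table 1 says that charges do not reflect the cost of care accurately, and the utility gains are assumed, so the per-QALY amounts are not forecasts. The endpoint is also secondary, has no formal hypothesis in section 10.2 and does not touch the primary analysis or the sample size.

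A gap remains after these concessions. Nothing requires both differences to appear beside the ratio, and separate models do not give the joint uncertainty of cost and effect. The sensitivity section recognises that a small effect difference inflates the ratio, but answers with another ratio.

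**Conclusion.** The concern holds as a gap in pre-specification and reporting for a named secondary endpoint. The chosen summary does not rank results in the quadrant the sponsor expects, and it comes with no rule for stating dominance and no joint uncertainty method. The ordering, equal-value and sign results are algebraic and need no assumptions beyond non-zero differences. The dollar figures and simulated chances are illustrative: they rest on a charge difference used in place of a cost difference, and on assumed utilities, SDs and independence of cost and effect. The plan should be amended before the analysis. Aim 1's primary comparison is unaffected.

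**What to change.** Amend the Cost-Effectiveness Analysis text in section 10.4.3 as follows.

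1. Report incremental cost and incremental QALYs separately, each with a 95% confidence interval.
2. If SSU is cheaper and better, or dearer and worse, state dominance in words and give no negative ratio.
3. Make incremental net monetary benefit, over a stated range of willingness-to-pay values, the summary of the endpoint. Resample cost and effect together by patient in a bootstrap, and show the result on the cost-effectiveness plane. An acceptability curve can be drawn from the same replicates.
4. Quote an ICER only when both differences have the same sign. When both are negative, label it as savings per QALY lost, because the reading reverses.
5. Replace the sentence that links a negative ICER to savings, and apply the same rules to the 90-day analysis.

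The cost is SAP wording, standard bootstrap code and a threshold range, which the documents do not give and the sponsor would have to state. No new data are needed. If a threshold range cannot be agreed, items 1, 2 and 4 alone would resolve the sign problem, and the joint bootstrap could still be shown on the plane.

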4.2.3 EXPLORATORY ENDPOINTS

1) Caregiver burden as measured by **Oberst Caregiving Burden Scale and Bakas Caregiving Outcomes Scale** ; 2) Cost-Effectiveness of the SSU AHF strategy of care at 90 days; 3) Resource utilization measured by the Modified Resource Utilization Questionnaire for Heart Failure (mRUQ-HF) 4) All cause mortality at 30 and 90 days 5) All cause re-hospitalization at 30 and 90 days; 6) Days alive and out of hospital at 90 days 7) HF Guideline adherence at 30 days

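### The QALY in the 30-day cost-effectiveness analysis is summed over whole years, takes survival from a quality-of-life conversion, and has no stated value for death

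*Combined protocol and SAP*

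**What the plan says.** Section 4.2.2 lists as a secondary endpoint "Cost effectiveness analysis between the two arms at 30 days". Section 4.2.3 adds an exploratory endpoint, "Cost-Effectiveness of the SSU AHF strategy of care at 90 days".

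The method is in section 10.4.3 under Cost-Effectiveness Analysis. On the cost side, "we will examine the total cost of patient care from the index ED visit (study enrollment) for a period of 30 days". On the effect side, "Effectiveness will be defined by SF-12 and SF-6D metrics of patient self-reported QOL". The QALY then enters: "Effectiveness in ICER computations is often measured using quality-adjusted life years (QALYs), defined as" a sum from t0 to Z of discount factor × preference weight q_t × P_t. P_t "is the probability of surviving to each year t" and delta "is the time-discounting factor". The limits t0 and Z, the discount rate and any weight for part of a year are not given.

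The SF-12 is to be converted to SF-6D "to generate the preference weights and probabilities necessary to conduct the cost-utility analysis". QALYs are then listed, beside SF-12 and SF-6D scores, among the outcomes to be modelled. All effectiveness models are to include a baseline score. The CEA sensitivity section repeats the ICER with SF-12.

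Three other places matter:
- The schedule of events (7.3.7) has the SF-12 before discharge and at follow-up, and not at screening or baseline.
- The KCCQ analysis in 10.4.3 sets the score to 0 for patients who die without a 30-day value, as one of three treatments of death. No such rule appears for SF-12, SF-6D or QALYs.
- Section 10.4.5 analyses incomplete data by multiple imputation under missing at random, and also reports results that ignore the missing data.

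**The concern.** Costs cover 30 days while the QALY formula moves in steps of a year, and the plan does not say how to reconcile the two. An analyst who has to produce QALYs and an ICER must choose a reading, and the readings differ by an order of magnitude. The trial is unblinded (10.6.1), so that choice could be made with results by arm in view.

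Survival has a separate problem. The formula needs P_t, and the stated source is a set of answers from living respondents. Vital status is collected at 30 and 90 days but is not linked to P_t. A patient who dies has no end-of-episode SF-12. With no death value stated, the only rule available is the general one in 10.4.5, which either leaves that patient out or imputes a utility as if the patient were alive. Section 2.3.1 itself names premature discharge as a risk, so an effectiveness measure that is silent on early death is a poor basis for comparing these two strategies.

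**Working it through.** The plan states no QALY, ICER or power figure for this endpoint, so there is nothing to reproduce. The check evaluates the formula as written over the stated horizon.

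**Inputs from the plan:** yearly step (10.4.3); 30-day episode (4.2.2, 10.4.3); 90-day exploratory horizon (4.2.3).

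**Assumed, for illustration only:** utility 0.60; day-30 difference between arms 0.02, with a range of 0.01 to 0.05; incremental cost +$500.

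**1. Time available.** 30/365.25 = 0.0821 year, so no patient can accrue more than 0.082 QALY in the episode. At 90 days the limit is 90/365.25 = 0.246.

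**2. Reading A: only the first term, t = t0.** The discount factor is 1 and P = 1, so the QALY equals the starting weight. At 0.60 every patient scores 0.60, whether alive or dead at day 30. As an example of what is missed, a death at day 15 at utility 0.60 forgoes 15/365.25 × 0.60 = 0.025 QALY; this reading counts 0.

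**3. Reading B: one yearly term filled with day-30 values.** The level at 0.60 is 0.600, against 0.60 × 0.0821 = 0.049 on the 30-day scale. The ratio is 365.25/30 = 12.2. At 90 days it is 365.25/90 = 4.06. If the follow-up survey falls at day 37, it is 365.25/37 = 9.9. Deaths do register here, but only if observed day-30 survival is put into P, which the plan does not say.

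**4. Difference between arms against an area under the curve.** Let both arms start at the same utility and let the day-30 mean (utility × survival) differ by d. Reading B gives d. A trapezoid gives (30/365.25) × d/2. The ratio is 2 × 365.25/30 = 24.35, whatever d is.

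| d (assumed) | Reading B | Area under the curve |
|---|---|---|
| 0.01 | 0.01 | 0.00041 |
| 0.02 | 0.02 | 0.00082 |
| 0.05 | 0.05 | 0.0021 |

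**5. Effect on the ICER**, with +$500 and d = 0.02:
- Reading B: 500/0.02 = $25,000 per QALY.
- Time-scaled day-30 weight: 500/(0.02 × 30/365.25) = about $304,000.
- Area under the curve: twice that, about $609,000.

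All three have the same sign.

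**6. Discounting.** At an assumed factor of 0.97 per year, 30 days gives 0.97^(30/365) = 0.9975. It can be dropped.

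**The case against.** The strongest reply is that the formula is textbook background, introduced by saying how effectiveness is often measured, and that the plan's own definition of effectiveness is the SF-12 and SF-6D scores. Much of this stands.

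- A reader might infer that the whole effect term is blind to quality of life. It is not. SF-12 and SF-6D are separate outcomes, the ICER is repeated with SF-12, and end-of-episode scores show change among survivors. The fault lies in the QALY term.
- A reader might infer that the plan commits a 12-fold error. It does not. No text says that a patient will be credited with a year; 12.2 is the result of one reading of an unadapted formula.
- A reader might infer that, on Reading A, randomization makes the arm difference pure noise. The schedule defeats this: the first SF-12 is taken after randomization and after treatment in each arm. Reading A also fits poorly with using the baseline score as a covariate.
- Deaths are not lost to the trial. They count in the primary endpoint, the safety analyses and the KCCQ analysis.
- The 90-day point is an inference: 10.4.3 describes only the 30-day episode and gives no separate formula for 90 days.

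What does not stand is treating the formula as decoration. QALYs are a listed outcome, a cost-utility analysis is planned, and no other QALY definition is given. The SF-12 and SF-6D scores do not repair the handling of deaths either, since no death value is stated for them.

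**Conclusion.** The point holds for the QALY term and for the missing death value. The plan gives a yearly formula for a 30-day analysis, names a source for survival that cannot provide it, and has no rule for patients who die. Depending on the reading, deaths and quality-of-life change within the episode add nothing, or QALYs are 12.2 times the time-scaled value at 30 days (4.06 at 90 days if the same formula is used there). For the between-arm difference the factor is about 24 against an area under the curve, on the assumption of equal starting utilities. These factors are arithmetic on the plan's horizons; the dollar figures rest on assumed inputs.

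A constant scale factor does not change the sign of the ICER. If short-stay care proves cheaper and better, as the plan expects, a scale error alone would not overturn that; the QALY differences and the ICER magnitude would still be wrong. The primary analysis and the sample size are unaffected. This should be corrected in the SAP before the cost-effectiveness analysis is run.

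**What to change.** Replace the yearly sum in 10.4.3 with a within-trial definition:

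- Each randomized patient's QALY is the area under the SF-6D curve from randomization to day 30, divided by 365.25, without discounting. Use the same definition over days 0 to 90 for the exploratory analysis.
- SF-6D is 0 from the date of death, using the vital status already collected. Deaths are not handled as missing data.
- Strike the statement that the SF-6D conversion supplies probabilities.
- Place each SF-6D score at its actual date and interpolate to day 30 from randomization. Follow-up is timed from discharge and has a window (7.3.3), so scores will not fall on that day.
- Set day-0 utility by one common rule for both arms, for example a single assumed value varied in a sensitivity analysis. This is needed because the first SF-12 comes before discharge, at different times by arm: under 24 hours for the short-stay strategy against a median inpatient stay of 4.3 days (6.1.1).
- Do not use the pre-discharge SF-12 as a baseline covariate, since it is measured after randomization.

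The cost is SAP wording, a little code and an assumed day-0 value; no new data are needed. Reported QALY differences will become much smaller.
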